Behavioral regulation/ impulsivity will be assessed via an abbreviated (9-item) version of the Monetary Choice Questionnaire developed by Kirby and Marakovic (Kirby & Maraković, 1995). Because yoga is proposed to increase self-regulation, we expect that the yoga group will improve on this measure to a greater extent than the MET group. A recent study found that older adults with MCI showed significantly greater delay discounting than healthy controls at the small reward magnitude, leading the authors to propose delay discounting as a candidate marker for early dementia (Lindbergh, Puente, Gray, Mackillop, & Miller, 2014). Because these results were only significant at the small reward magnitudes, we are only using the small reward magnitude items (i.e., items for which the delayed reward is less than or equal to \$35).

Measures of medical comorbidity. Comprehensive assessment of vascular and nonvascular medical burden will be provided using screening ECG and medical assessments and the review of medical documentation and will include the Stroke Risk Factor Prediction Chart (SRF)(Ho et al., 1993; Truelsen et al., 1994) of the American Heart Association for rating cerebrovascular risk factors (5 min). This scale incorporates eight independent measures; age, presence and treatment of hypertension, diabetes, smoking, coronary vascular disease, atrial fibrillation and left ventricular hypertrophy and provides a score indicating overall risk for cerebrovascular disease and stroke. The Cumulative Illness Rating Scale-Geriatric (CIRS-G)(Salvi et al., 2008) is used for rating the severity of chronic medical illness and burden in 14 organ-systems (15 min).

Family History of Dementia. Because family history of dementia is a known risk factor, this will be assessed in the form of a yes/ no question during the in-person screening. This variable will be added as a covariate and investigated as a possible moderator of treatment effects.

Physical Activity and Meditation Practice. Degree of physical activity and meditation practice will be assessed and used as covariates in analyses of treatment effects. For physical activity assessment, we will be using the short International Physical Activity Questionnaire modified for the elderly (IPAQ-E) (Hurtig-Wennlöf, Hagströmer, & Olsson, 2010).

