Pain will be assessed via the Brief Pain Inventory (BPI) Short Form, a validated scale for rapidly assessing the severity of pain and its impact on functioning (Cleeland, 1989).

Safety Evaluations: All participants will be interviewed about their recent history of psychiatric and medical illnesses, psychosocial stressors, and current medications. We will use the UKU Side Effect Rating Scale (Lingjærde, Ahlfors, Bech, Dencker, & Elgen, 1987), a rating scale for monitoring adverse events which will be completed at each assessment visit.

Domains of Assessment	Screen	Baseline	Week 6 (after class)	Week 12	Week 24	Week 48
Cognitive						
Clinical Dementia Rating	Х					
MMSE	Х			Х	Х	Х
Neuropsychological battery		Х			Х	Х
Memory Functioning	Х			Х	Х	Х
Psychosocial						
Beck Depression Inventory	Х			Х	Х	Х
Hamilton Anxiety	Х			Х	Х	Х
Perceived Stress Scale	Х			Х	Х	Х

Table 4. Assessment schedule.

Resilience (CD-RISC Scale)	х			x	x	x
Emotion Regulation	Х		Х	Х	Х	Х
SF-36 (QOL)	Х			Х	Х	Х
Duke Social Support	Х			Х	Х	Х
Monetary Choice	Х			Х	Х	Х
Medical						
CIRS-G	Х			Х		
Stroke Risk	Х			Х		
Clinical ECG	Х					
Brief Pain Inventory	Х			Х	Х	
Other						
Demographics / medical and reproductive history and medications	х					
Monitoring for new treatments		х	Х	X	Х	x
Treatment credibility		X (wk 2)		Х		
Clinical Global Improvement				X	х	x
Family history of dementia	Х					
Physical Activity and Meditation Practice	Х			Х	х	X
Adverse reactions		Х	Х	Х	Х	Х
Cellular Biomarkers						
Telomerase levels		Х		Х	Х	
Telomere length		Х		Х	Х	
Cardiac Biomarkers						
Lipid panel, hsCRP, HbA1c, TSH, electrolytes, CBC		x		х	х	
BP, HR, weight		Х		Х	Х	Х
Molecular Biomarkers						
Cytokine gene polymorphisms		x		x	х	
Microarrays (GWAS expression)		X		Х	х	
Imaging Biomarkers						
Structural MRI		Х		Х		
fMRI		Х		Х		
ANS Biomarkers						

Breathing rate	X	X	X	
End-tidal CO ₂	X	Х	Х	
ECG	X	Х	Х	
Continuous blood pressure	X	Х	Х	
Skin face temperature	X	X	Х	
Electromyogram	Х	Х	Х	
Spirometry	X	X	Х	
Galvanic skin response	X	Х	Х	
ANS challenges	X	X	Х	

Inflammatory biomarkers: Inflammatory signaling will be measured by assay of activation of NF-κB using intranuclear staining and flow cytometric analyses, given its associations with mood (Koo, Russo, Ferguson, Nestler, & Duman, 2010; Pace & Miller, 2009).

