Microarray-based genome-wide transcriptional analyses will be used identify the molecular inflammation-related signaling pathways that are plausible candidates for molecular mediators of inflammation (e.g., NF-B) (Cole, 2010; Irwin, Olmstead, & Motivala, 2008; Irwin, Wang, Campomayor, Collado-Hidalgo, & Cole, 2006) and

glucocorticoid receptor-related signaling pathways that may underlie increased inflammatory signaling (Cole et al., 2007; G. E. Miller et al., 2008) with measures performed at baseline, week 12, and at 6months, as described previously (Cole et al., 2007; G. E. Miller et al., 2008). Expression data will be subject to quantile normalization, with differentially expressed genes identified based on False Discovery Rate analyses controlling false positive errors at 5%, and subsequent TELiS bioinformatics analysis of GR target motifs within the promoters of genes up-regulated in KK+KY vs. MET. Confirmatory RT-PCR analyses will be conducted on a subset of 12 differentially expressed transcripts to confirm microarray indications (Cole et al., 2007; G. E. Miller et al., 2008). We will assess the activity of telomerase level and TL at baseline, weeks 12 and 6month follow-up to monitor changes. The protocol will be the same as the one used previously by Jacobs and colleagues (Jacobs et al., 2011). Quantification of telomerase activity will be measured from the extract using the telomeric repeat amplification protocol (TRAP) as previously described (Kim & Wu, 1997) with a commercial kit (TRAPeze®, Chemicon, Temecula, CA). We will assess other factors related to inflammation during our baseline assessment and throughout the trial (e.g., alcohol, smoking, BMI, physical activity; use of NSAIDs, and recent infections when samples are

		•	
Sequence #	Sequence type	Acquisition time	Protocol type
	1. Localizer		-21: -
1.1	Localizer	0:00:09	HCP
1.2	AAHScout	0:00:14	HCP
1.3	Localizer_aligned	0:00:21	HCP
	2. T1-weighted image)	
2.1	T1w setter	0:00:02	HCP
2.2	T1w MPR vNav 4e	0:08:22	HCP
	3. T2-weighted image)	
3.1	T2w setter	0:00:03	HCP
3.2	T2w_SPC_vNav	0:06:35	HCP
	4. Resting state fMR		
4.1	SpinEchoFieldMap_AP	0:00:09	HCP
4.1	SpinEchoFieldMap_PA	0:00:09	HCP
4.3	Cal_800TR	0:00:30	HCP
4.4	rfMRI_REST_AP	0:06:41	HCP
4.5	rfMRI_REST_PA	0:06:41	HCP
	5. tfMRI N-back task		
5.1	task fMRI N-back	010:00	HCP
5.2	SpinEchoFieldMap_AP	0:00:09	HCP
5.3	SpinEchoFieldMap_PA	0:00:09	HCP
	6. task fMRI face nami	ng	
6.1	task fMRI face naming	0:05:25	HCP

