Autonomic nervous system (ANS) and respiratory measures. In order to link genotype and neuroimaging data with respiratory and ANS functioning, we will perform a series of five tests: 1) rest; 2) paced breathing; 3) breath hold; 4) Valsalva maneuver; 5) hand grip. These tasks will provide detailed information about cardiorespiratory functioning. Continuous blood pressure will be assessed using a probe attached to two fingers of the same hand. An additional finger probe will be used to measure the Galvanic skin response (GSR) and chest electrodes will be applied for the electrocardiogram (ECG) and on the hand for an electromyogram (EMG). A respiratory belt around the patient's chest will provide breath rate data and a small probe attached to the cheek will measure changes in face skin temperature. End-tidal CO2 will be measured using a capnometer and spirometry will be used to investigate pulmonary capacity. Verbal instructions will be provided and a computerized task will indicate to the subjects when to begin and end each challenge, for example when to prepare for the breath hold (deep inhale followed by deep exhale and then hold at the top of the next deep inhale). Data will be recorded and time-locked using a BioPac system and associated software, which will also be used to process the data.

Randomization and treatment schedule:

After all screening and baseline test results are reviewed and eligibility criteria are confirmed, patients will sign the informed consent form. Next, participants will be randomized to either MET or KK+KY groups using a computer-generated random assignment scheme, which assigns participants in a 1:1 ratio to each group using a customized module built into the centralized data system. All behavioral raters will be blind to the group assignment, and participants will be asked not to disclose their group assignment to the raters.

Study intervention procedures:

Participants will be randomized to: (1) MET class for 60 minutes per week plus daily homework; or (2) KY class for 60 minutes per week plus daily KK homework. Participants will complete a questionnaire about their treatment expectations after their second class. Follow-up assessments immediately after the intervention (12 weeks) as well as at 24 and 48 weeks will test the effect of the interventions at both short- and long-term follow-up.

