Kirtan Kriya (KK). Participants will be asked to engage in 12 minutes of daily KK meditation. Meditations will be guided by standardized CDs distributed to participants that can be practiced at home. The protocol for KK is a standard ancient chanting meditation for the Kundalini Yoga practice as taught by Yogi Bhajan and as utilized in previous studies in older adults (Andrew B. Newberg, Wintering, Khalsa, Roggenkamp, & Waldmanb, 2012). The meditation involves repetitive finger movements or mudras, as well as chanting of the mantra "Saa, Taa, Naa, Maa," meaning "Birth, Life, Death, and Rebirth" first chanted aloud, then in a whisper, and silently for the total of 11 minutes with 1 minute allocated to "tuning in" at the beginning and the final deep breathing relaxation accompanied by the visualization of light.

Alternate treatments. All participants will be medically stable prior to entry into the study protocol. However, if participants engage in alternate treatments, they will be advised to inform the PI. Upon completion of the research procedures, yoga classes will be offered to participants who participated in MET and vice versa.

Treatment expectancy/ credibility. Our study has been designed to promote equal perception of treatment expectancy/ credibility between groups. We will evaluate treatment credibility, expectation for change, and satisfaction after the 2nd session of treatment and at post-intervention using a 10-point Likert scale, as we have done in our pilot study.

Dosing effects. We will distribute and collect home practice logs to determine the relationship between practice and outcomes. The extent to which participants continue to practice skills learned during the intervention period will also be assessed at 6-month and 12-month follow up. As in previous studies, we will also ask participants in both intervention groups to keep a brief weekly journal about any changes they have noticed that they attribute to the intervention. This data will be analyze through qualitative analysis at the completion of the study. **Data analysis.** Primary analyses will be carried out on an intent-to-treat basis; additional analyses considering dropout or other observable post-randomization outcomes will make use of an instrumental-variable analysis framework.

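### Does the missing time point for the physical-activity and meditation covariates put the treatment-effect analyses at risk?

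*Combined protocol and SAP*

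**What the plan says.** The paragraph on physical activity and meditation practice in Measures and Outcomes states: "Degree of physical activity and meditation practice will be assessed and used as covariates in analyses of treatment effects". It names the questionnaire for physical activity but no visit. The paragraph just before it, on family history of dementia, does fix the timing of its covariate: "this will be assessed in the form of a yes/ no question during the in-person screening".

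In Table 4 the row "Physical Activity and Meditation Practice" is marked at Screen, Week 12, Week 24 and Week 48. That gives one value before randomization and three after it.

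Meditation is also part of one assigned treatment. Study intervention procedures describes that arm as "KY class for 60 minutes per week plus daily KK homework", and the Kirtan Kriya paragraph adds: "Participants will be asked to engage in 12 minutes of daily KK meditation".

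Three other places bear on the question:

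- **Data analysis** opens with: "Primary analyses will be carried out on an intent-to-treat basis". The same sentence sends additional analyses of dropout and other post-randomization outcomes to an instrumental-variable framework.
- **Dosing effects** relates home practice to outcome and adds: "The extent to which participants continue to practice skills learned during the intervention period will also be assessed at 6-month and 12-month follow up".
- **Inflammatory biomarkers** says: "We will assess other factors related to inflammation during our baseline assessment and throughout the trial". Physical activity is one of the factors listed there.

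The mixed model in Data analysis has group, time and their interaction as fixed effects. The Primary outcome paragraph makes further covariates optional and refers back to the earlier text.

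**The concern.** The covariate sentence is unconditional, three of the four measurements come after randomization, and the analysis is a repeated-measures model. An analyst could enter the covariate visit by visit, and no sentence expressly forbids it.

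That choice would matter. In-trial meditation is something the KK+KY arm is asked to do, so holding it constant removes whatever part of the effect runs through practice. It can also do harm when practice has no effect at all: if motivation or general health drives both practice and test scores, comparing the arms at equal practice compares unlike participants. The estimate would then not be the intent-to-treat effect. If the choice were made after the data had been seen, it would also be a choice between two different estimands.

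**Working it through.** **1. The plan's own figure.** Power analysis gives 45 per group, an effect size of 0.60, two-sided 5% and 80% power for executive functioning. With within-arm SD 1, SE = sqrt(2/45) = 0.211. The noncentral t with 88 df gives power 80.4%, so the figure reproduces.

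**2. Screening values.** Randomization makes the expected arm difference in a screening covariate zero, so the expected group coefficient stays at 0.60. If the covariate predicts the outcome with a within-arm slope of 0.1 to 0.3 SD per SD (assumed), residual variance falls slightly. By the normal approximation, power is 82% to 85%, against 81% unadjusted by the same approximation. This reading does no harm.

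**3. In-trial values.** The documents give neither the arm–practice correlation r nor the within-arm practice–outcome correlation rho. Both are assumed here.

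- Arm difference in practice, in within-arm SDs: d = 2r/sqrt(1 − r²) = 0.873, 1.500 and 2.667 for r = 0.4, 0.6 and 0.8.
- Expected group coefficient: true difference − rho × d.
- SE = 0.211 × sqrt((1 − rho²)/(1 − r²)), with 87 df.

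Worked case, r = 0.6 and rho = 0.1: coefficient 0.60 − 0.1 × 1.5 = 0.45; SE = 0.211 × sqrt(0.99/0.64) = 0.262; power 40%.

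| | r = 0.4 | r = 0.6 | r = 0.8 |
|---|---|---|---|
| Shift, rho = 0.1 | −0.09 | −0.15 | −0.27 |
| Shift, rho = 0.3 | −0.26 | −0.45 | −0.80 |
| Power at 0.60, rho = 0 | 73% | 61% | 39% |
| Power at 0.60, rho = 0.1 | 60% | 40% | 16% |
| Power at 0.60, rho = 0.3 | 33% | 9% | 9% |
| Type I error, rho = 0.1 (common cause only) | 7% | 9% | 12% |
| Type I error, rho = 0.3 (common cause only) | 22% | 42% | 66% |

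At r = 0.8 and rho = 0.3 the expected estimate is 0.60 − 0.80 = −0.20, so rejections there are mostly in the wrong direction. A negative rho reverses the sign of the shift. If the arms do not differ in the covariate, there is no shift. These are single-time-point figures. Precision in the planned mixed model would also depend on the within-person correlation of practice, which the documents do not give, so no mixed-model figure is offered.

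**4. Which reading the plan supports.**

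- Only the screening value is available as a baseline covariate; Table 4 has no second pre-randomization measurement.
- An intent-to-treat primary analysis is consistent with adjustment for pre-randomization variables and inconsistent with adjustment for exposure.
- The instrumental-variable sentence gives post-randomization quantities a separate route, outside the primary analysis.
- The later measurements have other uses: continued practice at 6 and 12 months in Dosing effects, and in-trial physical activity in Inflammatory biomarkers. Their presence in Table 4 therefore does not imply time-varying adjustment.
- The covariates discussed in Data analysis are demographic variables compared by group, which are baseline quantities.

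**The case for a change.** The strongest case for a change is that none of this is an explicit rule. The intent-to-treat statement does not set covariate timing. The instrumental-variable sentence speaks of outcomes in additional analyses and does not name these two measures. The adjacent family-history paragraph shows that the authors could state a time point. One sentence would close the gap without touching data collection or models, and the consequences of the wrong choice are large in the table above.

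It stands that the time point is unwritten and that later values are not expressly excluded. The arithmetic also stands as an illustration. What does not stand is the step from there to a defect. No sentence says later values will be used, and the sections that bear on the choice favour screening values. The most striking figures need an arm difference of 2.67 SD in practice together with rho = 0.3. None is specific to physical activity, for which the documents give no expected arm difference. Nor is a clarifying sentence quite trivial: confining later values to dosing and instrumental-variable work would clash with the in-trial recording of physical activity under Inflammatory biomarkers unless that use were excepted.

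**Conclusion.** No change is called for. This is missing detail that an analyst can fill sensibly: screening values as covariates, and later values for the dosing, instrumental-variable and inflammation-related work already described. On that reading the expected group effect is unchanged, and the stated 80% power for executive functioning is kept or slightly improved.

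The losses shown for in-trial adjustment (power from 73% down to 9%; type I error from 7% up to 66% for rho of 0.1 or 0.3 from a common cause) rest on assumed correlations and on an analysis the plan does not say it will run. They explain why screening values are the right choice; they do not predict bias in this trial. No sample-size or power figure in the protocol depends on the point. The conclusion assumes that the analyst takes the intent-to-treat statement at its word. Confidence is high that the time point is unstated, and no effect on the results can be derived from the documents.

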AD has further been associated with abnormal respiratory functioning. For example, multiple studies have found impaired blood pressure responses to the Valsalva maneuver and impaired heart rate responses to the handgrip task (challenges for the autonomic nervous system) in AD (Jensen-Dahm et al., 2015). Other impairments included inspiratory and expiratory pressure, increasing the risk for more severe respiratory complications, and exercise-related cardiorespiratory functioning, including oxygen consumption and minute ventilation (Billinger et al., 2011; Burns et al., 2008; Sanches et al., 2014). A 29-year longitudinal study in originally healthy women found that poorer respiratory functioning in midlife was associated with an increased risk of developing AD later in life (Guo et al., 2007). Moreover, studies in young, healthy participants have demonstrated that the presence of the APOE-e4 allele is associated with abnormal brain and neurovascular functioning, blood pressure, heart rate and end-tidal CO_2 (Filippini et al., 2009; Suri et al., 2015). Respiration is closely linked to, and can affect cardiovascular functioning (Sasano et al., 2002). For instance paced breathing at 5.5 breaths per minute can increase heart rate variability and enhance feelings of relaxation in healthy individuals (I. M. Lin, Tai, & Fan, 2014).

It's possible the APoE4 genetic variant may present an increased risk for AD in women because of how it interacts with estrogen. Researchers believe that estrogen may have neuroprotective properties, as well as provide protection in the context of AD, particularly when it comes to defending cells against amyloid-beta toxicity (Viña & Lloret, 2010). As women undergo menopause, they experience declines in their level of estradiol, a form of estrogen produced by the ovaries that may have an impact on the brain. As such, cognitive changes and declines are common complaints during this time in a woman's life (Mitchell & Woods, 2011). In fact, data suggests that nearly half of all postmenopausal women report noticeable symptoms of cognitive decline,

including difficulties with memory, attention, and concentration. Women also share cognitive complaints during the transition itself. And it is possible the loss of estrogen support at this time is responsible (Morrison, Brinton, Schmidt, & Gore, 2006).

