Perceived stress will be assessed via the Perceived Stress Scale (PSS), a validated measure of the degree to which situations in one's life are appraised as stressful (5 min) (Cohen, Kamarck, & Mermelstein, 1994).

Resilience: the Connor-Davidson Resilience scale (CD-RISC), a measure of resilience (Connor & Davidson, 2003)(5 min) will be administered. We previously administered this measure in a sample of 337 adults over the age of 60 years; exploratory factor analyses identified the following four factors: grit, active coping self-efficacy, accommodative coping self-efficacy, and spirituality.

Emotion regulation will be assessed via the 15-item Mindful Attention Awareness Scale (MAAS) which is designed to assess open or receptive awareness of and attention to what is taking place in the present (Brown, 2003), as well as a 5-item measure of self-kindness (Neff, 2003) and a 6-item measure of rumination (Trapnell & Campbell, 1999), both of which were found to significantly mediate the effects of 6week mindfulness intervention on depressive symptoms (Boyle, Stanton, Ganz, Crespi, & Bower, 2017) (5 min).

Health-Related quality of life will be determined using the Medical Outcomes Study Short Form 36-Item Health Survey (SF-36) (Ware & Gandek, 1994), which comprises 8 scales: physical functioning, role limitations – physical, role limitations – emotional, energy, emotional well-being, social functioning, pain, and general health (15 min).

The 11-item Duke Social Support Scale (Koenig et al., 1993) will be used to assess subjective support (7-item Subjective Support Subscale) and objective support (4-item Social Interaction Subscale). Both subjective and objective social support have been associated with mental and physical health symptoms (sleep disturbance, depressive symptoms, and fatigue) in older adults (Choi, Irwin, & Cho, 2015). Existing research evidence suggests that yoga increases oxytocin (Jayaram et al., 2013); thus, it might be reasonable to expect that women assigned to yoga may experience greater decreases in subjective social isolation than women assigned to MET.

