Memory Enhancement Training Intervention. Patients will be informed that MET teaches specific memory strategies and has been shown to improve memory in adults with mild cognitive impairment. The standard detailed protocol for MET program is based on evidence based techniques that use verbal and visual association strategies and practical strategies for memory compensation (Gross et al., 2012; Verhaeghen et al., 1992). The MET program is manualized and includes components adapted from other effective memory training programs (Verhaeghen et al., 1992) such as: (1) Education about memory; (2) Preliminary instruction in the basic elements of memory strategies (i.e. "pre-training"); (3) Instruction in specific memory strategies; (4) Home practice with logs to track activity; (5) Addressing non-cognitive factors such as self-confidence, anxiety, and negative expectations; (6) Small (i.e. 10 persons) groups and short (60 min) sessions. The curriculum is divided into 12 weekly sessions which are organized in the same way in which trainers: (1) Document attendance, collect homework completion logs and assess engagement in alternative treatments; (2) Review the previous session's homework in order to reinforce home practice; (3) teach new techniques, reviews, and conduct in-class exercises, (4) assign homework for the upcoming week. Overall, in each session, roughly 15 minutes are devoted to reviewing the homework and 45 minutes is devoted to learning and practicing techniques. Specific techniques include: Visual associative learning strategies for learning faces and names (adapted from McCarty, 1980)(McCarty, 1980), verbal associative techniques such as the use of stories to remember lists: organizational strategies (categorizing items on a grocery list); forming good memory habits to recall where one places items, what one has done in the recent past (e.g. locking doors, turning off appliances); and how to remember future tasks (i.e., appointments). [name], a postdoctoral fellow supervised by [name], or a masters-level trainee supervised by [name] will teach the MET intervention.

KK+KY intervention:

Kundalini yoga (KY) class will be scheduled for 60 minutes weekly and will be conducted by a certified yoga teacher. The content and structure of the class will be similar across weeks: 1) Tuning in (5 minutes); 2) Warm up (10 minutes); 3) Pranayam (10 minutes); 3) Kriya (20 minutes); 4) Meditation (12 minutes) 5) Shavasana (3 minutes).

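### The week-6 emotion-regulation scales are given after class, so an arm difference at that one visit could mix a short-term session effect with lasting change (minor point, nearly free to fix)

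*Combined protocol and SAP*

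**What the plan says.** Table 4 (Assessment schedule) marks the row "Emotion Regulation" at screening, week 6, week 12, week 24 and week 48. The week-6 column is headed "Week 6 (after class". It is the only visit column defined by its relation to a class, although a note in the table and the intervention text also place a treatment-credibility rating after the second session. At week 6 the only other rows marked are monitoring for new treatments and adverse reactions, so emotion regulation is the only efficacy measure taken then.

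The measures section describes the emotion-regulation set as a 15-item mindful attention scale, five self-kindness items and six rumination items, about 5 minutes in all. The mindful attention scale is said to "assess open or receptive awareness of and attention to what is taking place in the present". The self-kindness and rumination items are supported by a cited study: "both of which were found to significantly mediate the effects of 6week mindfulness intervention on depressive symptoms".

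The section on the KK+KY intervention ends the 60-minute class with "4) Meditation (12 minutes) 5) Shavasana (3 minutes". In the section on MET, about 15 minutes go to homework review and "45 minutes is devoted to learning and practicing techniques", with new homework assigned.

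The text schedule under Measures and Outcomes lists baseline, week 12, and 6 and 12 months for all outcome measures. It does not mention week 6.

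**The concern.** Randomisation makes the arms comparable, but it does not make the conditions of measurement comparable. At week 6 one arm answers questions about present-moment attention, self-kindness and rumination after a session that closed with meditation and rest. The other arm answers them after memory work. If a session moves these answers for an hour or so, that movement is tied to arm and would appear in the week-6 contrast as if it were change in emotion regulation.

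The screening rating cannot separate the two, because it precedes any class. The ratings from week 12 onward are not scheduled by reference to a class, so week 6 also differs from the rest of its own series. No delay after class, pre-class rating or recall window is given, so nothing collected at week 6 would allow the two components to be pulled apart later.

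What is at stake is limited to how a mid-treatment value might be read: as an early gain in emotion regulation, or as a step on the way to later benefit.

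**Working it through.** **No stated figure to reproduce.** The plan gives no number for the week-6 rating, so the check rests mainly on setting its sections side by side.

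1. *Timing.* In Table 4, week 6 is after class. Screening, baseline and weeks 12, 24 and 48 have no such condition in their headings.
2. *What precedes the rating in the yoga arm.* The class segments are 5 + 10 + 10 + 20 + 12 + 3 = 60 minutes. The last 12 + 3 = 15 minutes are meditation and Shavasana.
3. *What precedes it in the MET arm.* About 15 + 45 = 60 minutes of homework review and technique practice.
4. *Could a short-term effect be expected?* The Introduction says that paced breathing can "enhance feelings of relaxation in healthy individuals". That makes a session effect conceivable, but it concerns relaxation, not these three scales.
5. *Is the week-6 value used?* The mixed models under Data analysis are introduced for cognitive functions. The Primary outcome paragraph names 12 weeks and 6 and 12 months, for cognitive domain scores. No section specifies a week-6 contrast, a model for emotion regulation, or a mediation analysis.

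**Illustration of size.** The inputs are:
- 45 per arm, from the Power analysis: 100 × (1 − 0.10) / 2 = 45. This is the 12-week completer number, and at week 6 it could be slightly higher.
- Two-sided alpha 0.05, from Data analysis.
- A shift of d standard deviations in one arm only, with no lasting effect. The documents give no value for d, so a range from zero is assumed.

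With n per arm, the noncentrality is d × √(n/2) = d × √22.5 = 4.743 d, and the t-test has 2n − 2 = 88 degrees of freedom (critical value 1.987). The probability of a significant unadjusted week-6 difference is then:

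| Assumed shift d (SD) | Noncentrality | Noncentral t | Normal approximation |
|---|---|---|---|
| 0 | 0 | 5.0% | 5.0% |
| 0.1 | 0.474 | 7.6% | 7.6% |
| 0.2 | 0.949 | 15.5% | 15.8% |
| 0.3 | 1.423 | 29.1% | 29.6% |
| 0.4 | 1.897 | 46.7% | 47.5% |

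The table is symmetric in the sign of d: it says how often a difference would be declared, not which arm would be favoured. It applies to a single unadjusted test at week 6, which the plan does not call for. A Bonferroni or Benjamini-Hochberg adjustment would lower every row.

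**The case against.** The strongest reply is that no planned analysis touches this value. The models are written for cognitive outcomes at other time points, the text schedule leaves week 6 out, and no aim or hypothesis concerns emotion regulation. That stands, and it is why the point is minor. It does not remove the point, because the data are collected with no stated use and no safeguard, and the choice of how to use them would be made after the fact.

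Three stronger readings are tempting, and the documents do not support them.

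- *A reader might infer that week 6 is biased toward KK+KY.* Nothing shows that these scales move after one class. Item wording and recall period are not given, and the description of the mindful attention scale states what it measures, not the period it covers. Direction is open too: the MET programme addresses self-confidence, anxiety and negative expectations, which could also shift self-ratings. Nor is an interval stated, so the rating need not come immediately after class.
- *A reader might infer that week 6 is meant as a mediator.* The cited 6-week programme is used to justify the choice of two scales. No mediation analysis of them is planned.
- *A reader might infer that these are secondary outcomes.* The named secondary outcomes are executive functioning and brain structure and connectivity. The paragraph on secondary clinical measures lists global impression, subjective memory, depression and anxiety scales. Emotion regulation has its own paragraph without that label.

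It is also fair to say that a pre-class rating is not free of all state effects, since the yoga arm meditates daily at home. Moving the rating removes only the difference created by the class itself, which is the part the schedule controls.

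**Conclusion.** The point holds as a narrow design remark. The week-6 emotion-regulation rating is taken under conditions that differ by arm and from the other visits in its series, so a difference at that visit could not be assigned to lasting change rather than to the session just finished. Whether a session effect exists, and its size and sign, are unknown. The range from 5% (no shift) to about 47% (0.4 SD) rests wholly on assumed shifts and on an unadjusted single-visit test.

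The reach is one non-primary domain at one visit. The primary memory outcome, the named secondary outcomes and the emotion-regulation ratings at weeks 12, 24 and 48 are unaffected. It is worth acting on because the change costs almost nothing and the mixing cannot be undone in analysis.

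**What to change.** - Give the week-6 emotion-regulation scales before class starts, in both arms, and change the Table 4 heading or add a footnote for that row. The adverse-reaction and new-treatment checks need not move.
- For women already rated after class, label week 6 as a post-session rating and report it descriptively by arm. Base any between-arm or mediation claim about these scales on week 12 onward.
- Reconcile the schedule sentence under Measures and Outcomes with Table 4, so that it is clear whether week 6 is an outcome visit for these scales and what the value is for.

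The cost is a 5-minute questionnaire moved from one end of the same class to the other, and a small edit to the table and text. There is no extra visit, and no change to the sample size or to any specified analysis.
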